## **Hypotheses**

**Hypothesis 1:** Education Webinar arm participants will improve during the course of the study on outcomes, including depression, anxiety, and burden.

**Hypothesis 2:** Individual Session arm, compared to the Education Webinar study arm, will be significantly more effective in improving outcomes, including depression, anxiety, and burden.

The effect of potentially confounding variables will be controlled for in analysis, i.e., determining whether impact is equivalent for participants who differ on a range of variables such as number of sessions completed, amount and type of care provided, and type of service member injury/disability.

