## **Technical Objectives**

**Objectives.** This randomized clinical trial will test a behavioral caregiving intervention that has been used successfully for dementia and SCI/D caregivers to provide services to stressed and burdened parent caregivers of OEF/OIF/OND service members. This intervention is six intensive individual sessions that will teach problem solving, cognitive restructuring and stress reduction targeted to an individual assessment of the care dyad's needs. It will be compared to another method of delivering content, education webinar sessions, which are analogous to the usual standard of care and will function as an attention control arm. The objective of the study is to determine which of these delivery mechanisms is more effective at helping parent caregivers of injured OEF/OIF/OND returning troops to improve their depression, anxiety, and burden, and to determine the feasibility of using individual sessions with this population of caregivers.

The long-term objective is to develop materials for parent caregiver interventions that can be disseminated across the Department of Defense (DoD) and the Department of Veterans Affairs (VA) Veterans Health Administration (VHA). Each of the interventions (the individual sessions and the education webinars) have different strengths, and may be more acceptable for different organizations and staff, according to varying logistic constraints and organization, patient, caregiver, and staff needs. Research goals include:

- 1) Determine effective strategies for providing education, skills building and support for parent caregivers of OEF/OIF/OND returning service members; and
- 2) Determine feasibility of conducting interventions with parent caregivers.

The technical aims of the study are: 1) determine characteristics of those who are recruited in the study arms; 2) determine satisfaction; 3) determine commitment and adherence to therapeutic recommendations; and 4) develop manuals for clinical translation.

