**Study Population and Inclusion and Exclusion Criteria.** The sample will be 160 stressed and burdened caregiver parents of post 9/11 service members. Participants will vary by race/ethnicity, age, region, rural/urban location, socioeconomic status, and service member rank and service branch, which will increase generalizability. To be eligible for the proposed study, the participant must: 1) identify as a parent who serves as the primary/main caregiver for an OEF/OIF/OND service member or veteran with a diagnosis of TBI or PTSD or physical injury and at least 1 ADL limitation or 2 or more IADL limitations; 2) provide 3 hours or more of care per day for at least 6 months; and 3) endorse at least 2 caregiving stress behaviors (overwhelmed, often needing to cry, angry/frustrated, cut off from family/friends, moderate/high levels of stress, and declining health). Caregiver exclusion criteria include: 1) current diagnosis of schizophrenia or other major mental illness; or 2) auditory impairment that would make telephone use difficult. We have used these criteria successfully in our dementia caregiver studies to identify a stressed population. For caregivers of post 9/11 veterans with high intensity care needs from polytrauma, 76% report spending more than 20 hours per week with 49% spending greater than 80 hours per week (15). In our work with post deployment spouses, spouses providing care for a service member who had injuries or diagnoses leading to care difficulty were more at risk for adverse outcomes and showed a stronger benefit from supportive interventions (57).

**Settings.** Caregivers will participate from home, anywhere in the country. The Interventionist will be at the VA Medical Center (VAMC) Memphis or at home for night or weekend sessions.

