### **Sample Size and Statistical Power**

Study participants will be randomly assigned to one of two arms: 1), the Individual Sessions arm, and 2) the Education Webinar arm. Hypothesis testing will compare Education Webinar arm pre-post outcomes, and Individual Sessions arm data to that of the Education Webinar arm. In accordance with the study hypotheses, our power analysis calculations are based on pretest-posttest gain score difference between contrast groups analyzed using repeated measures analysis of variance testing for a significant group by time interaction effect. Power analysis calculations use reliability data in estimating variance of gain scores (38,73,75). We base our power calculations on ANOVA because the “research on power analysis for mixed models is sparse” (105).

Power analysis assumptions used in computations included equal sample sizes in each contrast group of the study, equal variances and attrition in each contrast group, probability of Type I error of 0.05, non-directional testing of null hypotheses, and test-retest reliability as established by prior research (Table 2). Sample estimates of population parameters are assumed to be normally distributed with a mean error of zero. Accordingly, eighty or more subjects will be randomized to each arm of the study allowing attrition equal to 20% before the end of the study, which is the maximum we anticipate. This yields complete data for at least 60 caregivers in each arm of the study. More than 60 caregivers in a contrast group will increase statistical power above 0.80. The baseline data tabulated are values observed from our REACH and READI studies.

Table 2. Power analysis data.

Outcome Variable (Reference)	Baseline (M $\pm$ SD)	Reliability (r)	Power	Detectable Difference
Caregiver Measures				
Depression (PHQ-9) (73)	7.80 $\pm$ 5.94	0.84	0.80	1.78
Anxiety (GAD-7) (75)	7.61 $\pm$ 5.14	0.83	0.80	1.54
Burden (Zarit) (38)	17.56 $\pm$ 9.74	0.88	0.80	2.92

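### Hypothesis 1 tests uncontrolled pre-post change in the webinar (control) arm, so a significant result cannot be read as a webinar effect; the randomised comparison is unaffected

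*Combined protocol and SAP*

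**What the plan says.** The Hypotheses section lists two hypotheses. The first concerns the webinar arm alone: "Education Webinar arm participants will improve during the course of the study on outcomes, including depression, anxiety, and burden". The second is that individual sessions do better than webinars on the same outcomes. Sample Size and Statistical Power confirms that both are to be tested: "Hypothesis testing will compare Education Webinar arm pre-post outcomes, and Individual Sessions arm data to that of the Education Webinar arm".

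There is no third arm: "Study participants will be randomly assigned to one of two arms: 1), the Individual Sessions arm, and 2) the Education Webinar arm". Technical Objectives gives the webinar arm its role: "education webinar sessions, which are analogous to the usual standard of care and will function as an attention control arm".

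Under Methods, one entry condition is that caregivers "endorse at least 2 caregiving stress behaviors", and the plan explains the purpose of its criteria: "We have used these criteria successfully in our dementia caregiver studies to identify a stressed population". The description of the webinar arm accepts that expectancy and attention can produce improvement. Regression to the mean, natural course and repeated measurement are not mentioned anywhere.

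Technical Objectives also treats both arms as candidates for dissemination: "Each of the interventions (the individual sessions and the education webinars) have different strengths". The power section adds that a statistically significant comparison with d of 0.2 or more will count as clinically significant. It does not say whether that label covers Hypothesis 1.

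**The concern.** A within-arm test asks whether the mean moved, not why it moved. In this trial the arm under test is the one that is supposed to supply the reference for change without the active treatment, and nothing supplies a reference for it. Covariate adjustment and the mixed model do not help, because neither creates an untreated time trend for webinar participants.

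An effectiveness reading of a significant result is likely. The objectives present webinars as something that may be disseminated. The Background, discussing Table 1, already reads uncontrolled baseline-to-follow-up change in an earlier programme as benefit to caregivers. The d of 0.2 rule could attach a clinical label as well. One of the trial's two headline conclusions could then be a statement about webinars that the design cannot support.

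**Working it through.** **Inputs from the documents.** Table 2 gives baseline SD and reliability r: PHQ-9 5.94 and 0.84; GAD-7 5.14 and 0.83; Zarit 9.74 and 0.88. Testing is two-sided at 0.05. Eighty are randomised per arm with 20% attrition. The plan states at least 60 completers per arm; 80 × 0.8 = 64, so both are used where it matters.

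**Step 1: the plan's own figure.** The plan gives power only for the between-arm contrast (Hypothesis 2): about 0.30 SD, or 1.78, 1.54 and 2.92 points. The model is SD of gain = SD × √(2(1 − r)), and detectable difference = (1.960 + 0.842) × SD of gain × √(2/60). With r = 0.83 for all three outcomes this gives 1.77, 1.53 and 2.91, which matches the plan closely. With its own r, the PHQ-9 gives 1.72, so the stated 1.78 is slightly conservative. The same gain-score model can therefore be used for Hypothesis 1, for which the plan states no power or detectable change.

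**Step 2: smallest significant fall within the webinar arm.** Smallest fall = t(0.975, n − 1) × SD of gain / √n.
- PHQ-9: SD of gain = 5.94 × √0.32 = 3.36. At n = 60: 2.001 × 3.36/√60 = 0.87 points (0.146 SD). At n = 64: 1.998 × 3.36/8 = 0.84 points (0.141 SD).
- GAD-7: SD of gain = 5.14 × √0.34 = 3.00. At n = 60: 0.77 points (0.151 SD).
- Zarit: SD of gain = 9.74 × √0.24 = 4.77. At n = 60: 1.23 points (0.127 SD).

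All three lie below 0.2 SD. A PHQ-9 fall of 0.2 × 5.94 = 1.19 points would be significant and would also reach the d of 0.2 mark, if that mark were applied to within-arm change.

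**Step 3: illustration with no webinar effect.** Assume that the arm's mean falls by a fixed non-specific amount. This amount is an assumption; the documents give none. The chance that the paired t-test is significant in the direction of improvement (n = 60, noncentral t, Table 2 values) is:

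| Assumed fall | PHQ-9 | GAD-7 | Zarit |
|---|---|---|---|
| 0 SD | 0.025 | 0.025 | 0.025 |
| 0.1 SD | 0.27 | 0.26 | 0.34 |
| 0.2 SD | 0.77 | 0.74 | 0.88 |
| 0.3 SD | 0.98 | 0.98 | 1.00 |

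**Step 4: effect on Hypothesis 2.** A simulation (20,000 runs, n = 60 per arm, r = 0.84) gave both arms the same fall of 0.1, 0.2 or 0.3 SD. The webinar arm's own test was significant for improvement in 27%, 77% and 98% of runs. The between-arm test rejected in 4.9%, 5.0% and 5.1%, which is the nominal rate.

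**The case against.** The strongest reply is that Hypothesis 1 predicts improvement and does not say that webinars cause it. The comparative wording sits in Hypothesis 2 and in the main objective, and the mixed-effects section judges effectiveness by comparing slopes between arms. The plan calls webinars an attention control throughout and says why such a control can improve. All of this stands. The documents contain no rule that turns a significant Hypothesis 1 into a claim of webinar benefit. They also contain nothing to prevent one, and a test that cannot inform effectiveness has little reason to be one of two formal hypotheses.

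Two stronger readings are tempting, and the documents support neither.

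- A reader might infer that entry on stress makes a sizeable regression to the mean certain, and put a figure on it. The usual formula, (1 − r) × elevation × SD, needs direct selection on the outcome score and the elevation above the source-population mean. Here entry is on stress behaviours at screening, not on PHQ-9, GAD-7 or Zarit scores. Baseline is measured later, after mailed consent, so some regression may already have happened. Caregiving must also have lasted at least six months, so part of the elevation may be stable. The elevation is not given. Regression to the mean is a possible contributor of unknown size.
- A reader might infer that the extra within-arm tests raise the error rate of the randomised comparison. Step 4 shows that a drift shared by both arms leaves that rate at its nominal level. Hypothesis 1 is a separate question and cannot rescue a failed Hypothesis 2.

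**Conclusion.** The concern holds, but only for the interpretation of Hypothesis 1. As planned, a significant pre-post result in the webinar arm would not distinguish a webinar effect from time, retesting, attention or regression to the mean. The bar is low: 0.84 to 0.87 PHQ-9 points on the plan's own SD and reliability, assuming that the Table 2 r describes the correlation between baseline and follow-up. How often this would mislead depends on a non-specific fall that the documents do not quantify, and the illustrative range for the PHQ-9 runs from 2.5% at no fall to 98% at 0.3 SD. The randomised comparison stands as designed.

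**What to change.** In Hypotheses and in Sample Size and Statistical Power, relabel Hypothesis 1 as descriptive. Report change from baseline in each arm with 95% confidence intervals. State that within-arm change does not estimate a webinar effect and that the d of 0.2 clinical-significance label does not apply to it. Rest every effectiveness conclusion on the between-arm comparison, as the mixed-effects section already does.

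This changes wording only; sample size, randomisation and data collection stay as they are. The cost is giving up a claim of webinar benefit that the design cannot support.

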## **Technical Objectives**

**Objectives.** This randomized clinical trial will test a behavioral caregiving intervention that has been used successfully for dementia and SCI/D caregivers to provide services to stressed and burdened parent caregivers of OEF/OIF/OND service members. This intervention is six intensive individual sessions that will teach problem solving, cognitive restructuring and stress reduction targeted to an individual assessment of the care dyad's needs. It will be compared to another method of delivering content, education webinar sessions, which are analogous to the usual standard of care and will function as an attention control arm. The objective of the study is to determine which of these delivery mechanisms is more effective at helping parent caregivers of injured OEF/OIF/OND returning troops to improve their depression, anxiety, and burden, and to determine the feasibility of using individual sessions with this population of caregivers.

The long-term objective is to develop materials for parent caregiver interventions that can be disseminated across the Department of Defense (DoD) and the Department of Veterans Affairs (VA) Veterans Health Administration (VHA). Each of the interventions (the individual sessions and the education webinars) have different strengths, and may be more acceptable for different organizations and staff, according to varying logistic constraints and organization, patient, caregiver, and staff needs. Research goals include:

- 1) Determine effective strategies for providing education, skills building and support for parent caregivers of OEF/OIF/OND returning service members; and
- 2) Determine feasibility of conducting interventions with parent caregivers.

The technical aims of the study are: 1) determine characteristics of those who are recruited in the study arms; 2) determine satisfaction; 3) determine commitment and adherence to therapeutic recommendations; and 4) develop manuals for clinical translation.

## Project Milestones

Project Activities	Year 1	Year 2	Year 3
Develop Manual of Operations	*****		
IRB approval	*****		
Hire and Train Personnel	*****		
Recruitment	*****	*****	***
Interventions	*****	*****	*****
Collect Data	*****	*****	*****
Enter/Clean Data	*****	*****	*****
Analyze Results			*****
Prepare/Disseminate Results			*****

## Military Significance

Almost half (49.3%) of active military members are 25 years of age or younger, with the highest percentage of younger members in the Marines (68.5%), and 43.3% are unmarried, according to Military One Source (59). These young, single service members are often dependent on parents for any care they need post deployment (1), especially those returning with polytraumatic injuries (1-3) or traumatic brain injury, which can require long term rehabilitation under the care of a family member (4). To date, 103,792 service members have been diagnosed with PTSD and 253,330 with TBI. Injuries resulting from blasts are often polytraumatic (injuries to multiple body systems) (1,13). However, care needs may be at different levels, ranging from full time, 24/7 care needed for polytrauma/TBI injuries to supervision of risky behavior to assistance with reintegration challenges due to PTSD. Economically, the toll is high with treatment cost estimates for 2020 estimated to be \$8 billion annually. Personally, PTSD caregivers' care burden is twice that of other caregiving populations and is similar to that of dementia and chronic schizophrenia caregivers (60) with care provision upwards of 80 hours per week and care more likely to last longer than 10 years.

Carlson et al. found that caregivers with higher levels of depression, anxiety, or any physical health problems increased the chance of subsequent injuries to the patient (29). Service members returning with TBI made less progress in treatment if the family unit was distressed (18). Conversely, PTSD symptoms often decrease as family and social support increases (19). Providing education and mental health resources to families can help reduce caregiver burden, which in turn positively affects the health of the care recipient (27,28). Improving caregiver social support also improves outcomes for both (1,15).

This proactive approach to military family service delivery would remove or mitigate several barriers to care: lack of local services, access, privacy concerns, distance, and travel. By offering low-cost preventive interventions reflective of the public health model, these interventions would offer an alternative to centralized services that may not be used by military families, particularly those in rural areas and/or in the Guard/Reserve. In addition, parents may not be eligible for services from traditional military and veteran sources. The proposed interventions are focused on prevention and will be delivered to participants at high-risk for diminished general well-being related to depression, anxiety, and role strain/overload, to boost their self-efficacy and coping behaviors. With limitations of distance and transportation removed, this study is designed to increase access to services and to take the intervention to the people who need it most – parent caregivers who are experiencing difficulties providing post deployment care.

In addition, this study tests a model of delivery that could function well in multiple clinical and support settings of DoD and VA and is currently being implemented nationally for different populations by VA and community clinicians and social service providers. The individual sessions may provide an opportunity for participants to build skills and focus on topics of immediate interest one-on-one with an

Interventionist. For DoD and VA clinicians or individuals who would be providing the interventions, the ability to work with caregivers in person or remotely would meet different clinical goals and maximize staff flexibility. The intervention has the capability of activating formal and informal networks of support that can improve individual and family outcomes, and more importantly, build the capacity of the individuals and the military to meet future challenges (61).

VA and DoD resources are limited. The study will offer this under-served demographic of parents post deployment support. The intervention uses empirically proven components (problem solving, cognitive restructuring, stress management). The individual sessions have been shown to be an efficient intervention with stressed caregiving populations that improves outcomes and could be a low cost way to offer practical help to military families. Because the military and VA system may not be always available to work with parent caregivers, the REACH design, training, and materials empower caregivers with knowledge and skills to manage ongoing caregiving challenges.

## **Public Purpose**

Parents of adult and younger children who have acquired traumatic head injury will benefit from the findings of this research. Family concerns are similar, whether the injury is acquired in combat or the community, focusing on financial and social stressors (61), disruption to the family system (31), lack of emotional support (33), and need for information, particularly addressing behavioral, affective and quality of life changes of the head-injured person (33).

Community caregivers report high levels of caregiver distress (32), and high levels of unhealthy functioning (26). Depression, anxiety, and somatic symptoms are common among caregivers (26,62). Distress levels among spouses, parents, and other caregivers are comparable (26); however, parents are more distressed by fear of the future and physical burdens than spouses (33), and that fathers report greater injury-related stress and distress than mothers over time (63). Some of the stress of caregiving is related to the patient's characteristics. Higher caregiver distress is associated with caring for survivors who have worse functional status, receive more supervision, are less satisfied with life, and use alcohol excessively (26). Conversely, poorer caregiver functioning is associated with poorer patient functioning. For example, decreased patient participation in society is associated with a passive coping style by the primary caregiver (64).

Family coping and functioning are frequently strained for parents after a head injury. Mothers report family difficulties in getting along with each other, facing new financial hurdles, going separate ways as the family copes, and the family splitting apart (34). For parents of young children who have been injured there are differences between parents, with fathers more likely to use denial to cope while mothers are more likely to use acceptance and emotion-focused strategies (63).

There has been little comprehensive research (31) to determine what makes head injury caregivers depressed (32) and what caregivers need (33). Information concerning emotional and behavioral changes subsequent to head injury for family members should help families adapt better. Caregivers' needs can be more fully met by a combination of addressing common themes and the identification of individual family needs (33). Other families have expressed a desire for increased peer support (61).

Thus, this research will provide benefit to military, veteran and civilian parents struggling with the needs of their injured children.

## **Methods**

**Overview.** This randomized clinical trial will study a well-established intervention to provide education, training in coping skills (problem solving, cognitive restructuring, stress management), and support to parent caregivers of military personnel to an attention control arm. Both interventions have been used successfully in our work with military and veteran family members and caregivers. Study arms include:

1) individual telephone sessions with caregivers; and 2) education webinar sessions, analogous to usual care. There will be 80 parents recruited and randomized in each study arm, for a total of 160. A Caregiver Workbook will include comprehensive materials for all sessions and topics. All sessions will be taped and treatment fidelity will be monitored and ensured through assessment of intervention delivery, receipt, and enactment.

Outcomes will include depression, anxiety, and burden. Trained Research Associates will collect data by telephone at baseline, 3, and 6 months. Participant satisfaction will be measured with a project evaluation focused on benefit, utility and support.

**Study Population and Inclusion and Exclusion Criteria.** The sample will be 160 stressed and burdened caregiver parents of post 9/11 service members. Participants will vary by race/ethnicity, age, region, rural/urban location, socioeconomic status, and service member rank and service branch, which will increase generalizability. To be eligible for the proposed study, the participant must: 1) identify as a parent who serves as the primary/main caregiver for an OEF/OIF/OND service member or veteran with a diagnosis of TBI or PTSD or physical injury and at least 1 ADL limitation or 2 or more IADL limitations; 2) provide 3 hours or more of care per day for at least 6 months; and 3) endorse at least 2 caregiving stress behaviors (overwhelmed, often needing to cry, angry/frustrated, cut off from family/friends, moderate/high levels of stress, and declining health). Caregiver exclusion criteria include: 1) current diagnosis of schizophrenia or other major mental illness; or 2) auditory impairment that would make telephone use difficult. We have used these criteria successfully in our dementia caregiver studies to identify a stressed population. For caregivers of post 9/11 veterans with high intensity care needs from polytrauma, 76% report spending more than 20 hours per week with 49% spending greater than 80 hours per week (15). In our work with post deployment spouses, spouses providing care for a service member who had injuries or diagnoses leading to care difficulty were more at risk for adverse outcomes and showed a stronger benefit from supportive interventions (57).

**Settings.** Caregivers will participate from home, anywhere in the country. The Interventionist will be at the VA Medical Center (VAMC) Memphis or at home for night or weekend sessions.

